4.1 Inclusion criteria

Patients eligible for inclusion in this study have to fulfill **all** of the following criteria:

1. Patient must be able to understand and communicate with the investigator and comply with the requirements of the study and must give a written, signed and dated informed consent before any study assessment is performed
2. Male or non-pregnant, non-lactating female patients at least 18 years of age
3. Diagnosis of PsA classified by CASPAR criteria and with symptoms for at least 6 months with moderate to severe PsA who must have had at Baseline ≥ 3 tender joints out of 78 and ≥ 3 swollen joints out of 76 (dactylitis of a digit counts as one joint each)
4. A target psoriatic skin lesion and a PASI score of 1 or greater
5. RF and/or Anti-cyclic citrullinated peptide (anti-CCP) antibodies negative at screening.
6. Patients who are regularly taking NSAIDs as part of their PsA therapy are required to be on a stable dose for at least 2 weeks before study randomization and should remain on a stable dose up to Week 16
7. Patients taking corticosteroids should be on a stable dose of ≤ 10 mg/day prednisone or equivalent for at least 2 weeks before randomization and must remain on a stable dose up to Week 16
8. Patients taking MTX (≤ 25 mg/week) are allowed to continue their medication if the dose is stable for at least 4 weeks before randomization and must remain on a stable dose up to study completion
9. Patients on MTX must be on folic acid supplementation at randomization
10. Patients who are on a DMARD other than MTX must discontinue the DMARD 4 weeks prior to randomization visit except for leflunomide, which should be discontinued for 8 weeks prior to randomization unless a cholestyramine washout has been performed.

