6.4.10 Minimal disease activity

The proportion of patients achieving minimal disease activity (MDA (Coates 2010) (5 of the 7 following: ≤ 1 tender joint count, ≤ 1 swollen joint count, PASI ≤ 1 or IGA ≤ 1 , patient pain VAS ≤ 15 , patient global VAS ≤ 20 , HAQ-DI ≤ 0.5 , tender enthesal points ≤ 1).

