8.5 Adjudication Committee

Not required.

9 Data analysis

A designated Contract Research Organization will perform the statistical analysis.

It is planned that the data from all centers that participate in this protocol will be combined, so that an adequate number of patients will be available for analysis.

Unless otherwise specified, all statistical tests will be conducted against a two-sided alternative hypothesis, employing a significance level of 0.05.

Efficacy, safety, and other data will be summarized. For continuous variables, summary statistics (mean, standard deviation, median, 25th and 75th percentiles, interquartile range, minimum, and maximum) at each time point and for change from baseline to each time point will be reported by treatment group.

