9.5 Analysis of secondary variables

9.5.1 Efficacy variables

The secondary efficacy variables are the following:

1. Dactylitis (yes, no)

[figure not shown]
2. Enthesitis (yes, no)
3. ACR50 response (yes, no)
4. ACR70 response (yes, no)
5. Minimal Disease Activity (yes, no)
6. PASI75 response (yes, no)
7. PASI90 response (yes, no)
8. PASI100 response (yes, no)
9. Change from baseline in DAS28-CRP
10. Change from baseline in PASDAS
11. Change from baseline in SF12
12. Change from baseline in HAQ-DI

[figure not shown]
Two analyses of dactylitis and enthesitis (secondary efficacy variables 1 and 2) will be performed at each time point. For the first analysis, the data for the subgroup of patients who have dactylitis at baseline will be used (similarly for enthesitis) and the analysis of the binary response variable (yes, no) will be similar to the analysis of secondary efficacy variables 3-8 below. In the supporting analysis, the data for all patients will be used and an ordinal variable will be created based on presence (yes) or absence (no) of dactylitis at baseline and a post-baseline visit (similarly for enthesitis). The three categories for the ordinal variable will be no/no (category 1), no/yes and yes/no (category 2), and yes/yes (category 3). This ordinal response variable will be analyzed using a proportional odds regression model with treatment (3 treatment groups), methotrexate usage at baseline (yes, no), and body weight as explanatory variables (Stokes, Davis, and Koch, 2012). The odds ratios for each dose of secukinumab versus placebo, 95% confidence intervals for the odds ratios, and p-values based on the fitted model will be reported.

Secondary efficacy variables 3-8 will be analyzed at each time point using a logistic regression model with treatment (3 treatment groups), methotrexate usage at baseline (yes, no), and body weight as explanatory variables (Stokes, Davis, and Koch, 2012). The odds ratios for each dose of secukinumab versus placebo, 95% confidence intervals for the odds ratios, and p-values based on the fitted model will be reported.

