9.7 Sample size calculation

The sample size was calculated based on the primary efficacy variable (i.e., ACR20 response) for the primary comparison (i.e., secukinumab 300 mg versus placebo). ACR20 response rates of 50% for secukinumab 300 mg and 20% for placebo (corresponding to an odds ratio of 4) at Week 16 were assumed, based on results from AIN457F2312 (FUTURE 2) study. Using a continuity-corrected chi-squared test, an allocation ratio of 2:1, a two-sided significance level of 0.05, and a power of 0.90, approximately 88 patients in secukinumab 300 mg group and 44 patients in placebo group will be needed (nQuery Advisor 7.0). Assuming a loss to follow-up rate of 10% and a 2:2:1 allocation ratio (secukinumab 300 mg: secukinumab 150 mg: placebo), the total number of randomized patients will be approximately 250 (100 on secukinumab 300 mg, 100 on secukinumab 150 mg, and 50 on placebo)

10 Ethical considerations

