Minimal Disease Activity response at each time point up to Week 16 will be analyzed using a logistic regression model with treatment (3 treatment groups), methotrexate usage at baseline (yes, no), and body weight as explanatory variables. The odds ratios for each dose of secukinumab versus placebo, 95% confidence intervals for the odds ratios, and p-values based on the fitted model will be reported.

Number and percentages of Minimal Disease Activity response will be reported for each treatment group and by visit in entire treatment period up to Week 52. Similar summary will be provided for Minimal Disease Activity response using non-responder imputation method.

Very Low Disease Activity

Very Low Disease Activity (yes, no) is achived when 7 out of the following 7 criteria are met: ≤ 1 tender joint, ≤ 1 swollen joint, PASI ≤ 1 or IGA mod 2011 ≤ 1 , patient assessment of pain (0-100 Visual Analog Scale (VAS)) ≤ 15 , patient global assessment of disease (VAS) ≤ 20 , HAQ-DI ≤ 0.5 , tender entheseal points ≤ 1 .

Very Low Disease Activity response at each time point up to Week 16 will be analyzed using a logistic regression model with treatment (3 treatment groups), methotrexate usage at baseline (yes, no), and body weight as explanatory variables. The odds ratios for each dose of secukinumab versus placebo, 95% confidence intervals for the odds ratios, and p-values based on the fitted model will be reported.

Number and percentages of Very Low Disease Activity response will be reported for each treatment group and by visit in entire treatment period up to Week 52 for the observed data. Similar summary will be provided for Very Low Disease Activity response using non-responder imputation method.

PASI75, PASI90, PASI100 responses

Response to PASI75, PASI90, PASI100 at each time point up to Week 16 will be analyzed using a logistic regression model with treatment (3 treatment groups), methotrexate usage at baseline (yes, no), and body weight as explanatory variables. The odds ratios for each dose of secukinumab versus placebo, 95% confidence intervals for the odds ratios, and p-values based on the fitted model will be reported.

Novartis	For business use only	Page 28
SAP		Secukinumab/AIN457FUS01

The above analyses will be done on Psoriasis Subset.

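### The Minimal Disease Activity model has no baseline severity term, although the endpoint is scored on absolute cut-offs: a valid test that gives up a little precision and is cheap to improve

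*SAP*

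**What the plan says.** The SAP (2.7.2, Minimal Disease Activity) states: "Minimal Disease Activity response at each time point up to Week 16 will be analyzed using a logistic regression model with treatment". The remaining terms are methotrexate use at baseline and body weight. Protocol 9.5.1 agrees: "Secondary efficacy variables 3-8 will be analyzed at each time point using a logistic regression model with treatment (3 treatment groups), methotrexate usage at baseline", again with body weight, and MDA is variable 5 in that list.

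Protocol 6.4.10 defines MDA as five of seven items: at most one tender joint, at most one swollen joint, PASI or IGA at most 1, and then "patient pain VAS ≤ 15 , patient global VAS ≤ 20 , HAQ-DI ≤ 0.5 , tender enthesal points ≤ 1". All seven are levels at the visit; none is a change from baseline.

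Entry sets a floor on some items only. Under protocol 4.1 patients "must have had at Baseline ≥ 3 tender joints out of 78 and ≥ 3 swollen joints out of 76" and need a PASI of 1 or more. Pain, patient global, HAQ-DI and entheseal points have no floor.

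DAS28-CRP, PASDAS, SF12 and HAQ-DI change are modelled with their baseline value (SAP 2.7.2 and 2.11). SAP 1.1 states that randomization is not stratified.

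**The concern.** ACR20 and PASI75 are measured against the patient's own starting point. MDA is not. Two patients with the same improvement can differ on MDA because one started closer to the cut-offs. With no entry floor on four of the seven items, that distance can vary widely between patients, and nothing in the model accounts for it.

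Two things are at stake. First, a covariate that predicts the outcome usually raises power in a logistic model, and here none is used. Second, the placebo arm has about 50 patients and no stratification, so a chance difference in starting severity passes into the MDA odds ratio unadjusted.

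**Working it through.** **1. The plan's own figure.** The trial is powered only on ACR20: "ACR20 response rates of 50% for secukinumab 300 mg and 20% for placebo". The method is "Using a continuity-corrected chi-squared test, an allocation ratio of 2:1, a two-sided significance level of 0.05, and a power of 0.90", giving "approximately 88 patients in secukinumab 300 mg group and 44 patients in placebo group will be needed". With p0 = 0.2, p1 = 0.5, r = 2 and pooled rate (0.2 + 2 × 0.5)/3 = 0.4:

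- Uncorrected placebo n = [1.960 × √(3 × 0.4 × 0.6) + 1.282 × √(2 × 0.16 + 0.25)]² / (2 × 0.3²) = 38.4, so 39.
- Continuity-corrected n = (38.4/4) × [1 + √(1 + 6/(2 × 38.4 × 0.3))]² = 43.3, so 44 on placebo and 88 on 300 mg.
- Dividing by 0.9 gives 49 and 98, rounded in the plan to 50 and 100.

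The figure reproduces. No rate or power is stated for MDA, so everything below about its size is assumption.

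**2. Would yes/no MDA status at baseline help?** An eligible patient has at least 3 tender and 3 swollen joints, so both joint items fail and 7 − 2 = 5 items remain. Such a patient is in MDA at entry only by meeting all five, including PASI of exactly 1 or IGA at most 1. Status is therefore constant or nearly so.

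- If 1% were in MDA at baseline and 30% at Week 16, the largest possible correlation between the two is √[0.01 × 0.70/(0.30 × 0.99)] = 0.15. A correlation of 0.5 would need 9.7% already in MDA at entry.
- Simulated power for 300 mg against placebo (50/100/100 patients, assumed 10% v 30%, latent correlation 0.5) goes from 80.9% to 81.4% if 1% are in MDA at baseline, and to 82.8% if 5% are. At 20% v 40% it goes from 69.8% to 70.3% and 71.6%.

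The gain is about half a point at 1% and under 2 points at 5%.

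**3. Would a graded baseline measure help?** The number of criteria met at baseline runs from 0 to 5 in eligible patients and does vary. The check used a latent baseline severity correlated with latent Week 16 severity, MDA set by an arm-specific threshold, and five noisy dichotomised items summed to a count. Each model was tested by a two-sided 0.05 Wald test of 300 mg v placebo, with and without the count. Assumed MDA rates were 8-12% on placebo and 25-30% on active.

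| Latent correlation | Power gain from the count (points) |
|---|---|
| 0.3 | about 1-2 |
| 0.5 | about 3-5 |
| 0.6 | about 4-6 |

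A continuous average of the items gains slightly more: about 3.5-5.3 points at 0.5 for 10% v 30%. The ceiling is a score that captures baseline severity without error. It gains 5.1-7.0 points at 0.5 when unadjusted power is 59-87%, 1.9-2.5 points when that power is already 94-96%, and 1.0-2.6 points at 0.3.

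**4. Room for chance imbalance.** For a standardised baseline measure, the standard error of the difference between 100 and 50 patients is √(1/100 + 1/50) = 0.173 SD. Differences of 1.96 × 0.173 = 0.34 SD or more therefore arise by chance in about 1 trial in 20.

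**5. Are the items available at baseline?** The schedule table (protocol Table 6-1) is incomplete in the text available to me, so I inferred this from other endpoints. ACR response needs baseline joint counts and draws on baseline pain, patient global and HAQ. HAQ-DI change needs baseline HAQ-DI. The baseline-enthesitis subgroup needs entheseal data. PASI75 needs baseline PASI. The weak spot is the skin item: protocol 6.4.14 and 6.4.15 limit PASI and IGA to patients with at least 3% of body surface affected, while inclusion criterion 4 requires a PASI from everyone.

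**6. Can the model carry one more term?** At 10%/30%/30% there are 5 + 30 + 30 = 65 events for five slopes (two treatment terms, methotrexate, weight, baseline), or 13 per slope.

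**The case against.** The best reply is that this is a preference and not an error. Protocol and SAP agree, all binary secondary variables use the same covariates, SAP 2.6 names no key secondary objective, and power was planned only for ACR20. The confidence interval already allows for chance imbalance under randomization. The contrast with the ANCOVA endpoints is weak, because a baseline term is routine when change is the outcome. A covariate added after the Week 16 lock restores no confirmatory power, and a logistic model drops patients with a missing covariate. All of this stands. It sets the severity and shapes the fix, but it does not remove the gain in precision.

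A reader might also infer three stronger points, which the documents do not support:

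- **That leaving out baseline MDA status costs several points of power.** Step 2 shows that status is almost constant in eligible patients. Patients who breach the joint-count criterion stay in the analysis (SAP 5.5), so a stray case is possible, but this does not change the result.
- **That the planned test is biased or invalid.** It is a valid randomized comparison.
- **That the omission contradicts the rest of the SAP.** No passage commits the plan to baseline adjustment for MDA.

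**Conclusion.** The point holds as a minor efficiency improvement. MDA is an absolute-threshold endpoint modelled without any measure of where patients start, in an unstratified trial with about 50 placebo patients. The gain from a graded baseline count is modest and depends on the correlation, from about 1-2 points of power at 0.3 to 4-6 at 0.6. It rests on assumed MDA rates and latent correlations, on assumed item properties, and on equal rates in the two active arms. None of these is in the documents. It also rests on the inference that the component items are collected at baseline. If the true correlation is near 0.3, the benefit is close to negligible.

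**What to change.** 1. Keep the planned MDA model as it stands. Beside it, report the same model with one graded baseline covariate: either the number of MDA criteria met at baseline, or a continuous score from pain, patient global, HAQ-DI and entheseal points. The SAP revision history places these updates after the Week 16 lock, so label the adjusted model as added later.
2. State a rule for a missing skin item, for example by building the covariate from the non-skin items only, and a rule for any other missing baseline item. No patient should leave the Full Analysis Set because of the covariate.
3. Tabulate by arm the number of criteria met at baseline, including anyone already at five of seven.
4. If Very Low Disease Activity is modelled, use the same covariate. It requires seven of seven, so events will be fewer and the non-convergence and separation fallbacks in SAP 5.4.1 may be needed.

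Cost: SAP wording, one derived variable and one table, with no new data. The adjusted model spends one degree of freedom, and its odds ratio is conditional on baseline severity, so it is not directly comparable in size with the planned one.

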2.7.3 Handling of missing values/censoring/discontinuations

Patients who discontinued prematurely for any reason will be considered non-responders from the time they discontinued. Patients who do not have the required data to compute ACR response (i.e., tender and swollen joint counts and at least three of the five ACR domains) at baseline and at the specific time point will be classified as non-responders. For all other binary variables, non-responder imputation will be applied.

Missing data for continuous variables will be imputed using the last-observation-carried-forward (LOCF) method.

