For patients who discontinue study treatment prematurely for any reason before the end of **Treatment Period 1**, (Visit 10/Week 16 EOT1) must be performed approximately four weeks after the last dose of study treatment (secukinumab 300 mg, secukinumab 150 mg or placebo). Patients should also be contacted via telephone, 84 days (12 weeks) after last dose of study drug, to inquire about any AE/SAEs that occurred during this period.

For patients who discontinue study treatment prematurely for any reason before the end of **Treatment Period 2**, (Visit 19/ Last visit EOT2) must be performed approximately four weeks after the last dose of study treatment (300 mg or 150 mg s.c. secukinumab). Patients should also be contacted via telephone, 84 days (12 weeks) after last dose of study drug, to inquire about any AE/SAEs that occurred during this period.

If patients refuse to return for these assessments or are unable to do so, every effort should be made to contact them or a knowledgeable informant by telephone to determine the reason.

At a minimum, patients will be contacted for safety evaluations during the 84 days (12 weeks) following the last study visit or following the last administration of study treatment (whichever is later), including a final contact at the 84-day point. Documentation of attempts to contact the subject should be recorded in the source documentation.

AE/SAE information obtained as a result of these calls must be recorded in the eCRF.

Unscheduled visits

Patients may be seen at any time for an unscheduled visit, e.g., if they experience deterioration or AEs that in the opinion of the investigator/qualified site staff need intervention or repeat laboratory testing. The assessment(s) performed at an unscheduled visit must include at minimum: an assessment of concomitant medication and procedures/significant non-drug therapies, vital signs, and an AE/SAE assessment. Any additional assessments performed are at the investigator/qualified site staff's discretion. During an unscheduled visit, study treatment will not be administered.

Table 6-1 Assessment schedule

Period	SCR ¹		Treatment Period 1								Treatment Period 2									Unscheduled Visit	
Week	-8 to BL		BL	1	2	3	4	8	12	16/EOT	20	24	28	32	36	40	44	48	52/EOT		Day 84 Safety Follow-up ⁴
Visit No	1	2	3	4	5	6	7	8	9	10	11	12	13	14	15	16	17	18	19		
Visit Window (days) ²				+/-2	+/-2	+/-2	+/-2	+/-2	+/-2	+/-2	+/-7	+/-7	+/-7	+/-7	+/-7	+/-7	+/-7	+/-7	+/-7		
Assessments																					

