Secondary efficacy variables 9-12 will be analyzed at each time point by an analysis of covariance (ANCOVA) model with treatment (3 treatment groups), baseline, methotrexate usage at baseline (yes, no), and body weight as explanatory variables. The least squares means of the three treatment groups, least squares mean differences between each dose of secukinumab and placebo, 95% confidence intervals for the difference between each dose of secukinumab and placebo, and p-values based on the fitted linear model will be reported. Missing data will be imputed using the last-observation-carried-forward (LOCF) method.

Analyses of the secondary efficacy variables will be based on the Full Analysis Set.

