2.5.3 Handling of missing values/censoring/discontinuations

Patients who discontinued prematurely for any reason will be considered non-responders from the time they discontinued. Patients who do not have the required data to compute ACR20 response (i.e., tender and swollen joint counts and at least three of the five ACR components) at baseline and at the specific time point will be classified as non-responders.

In an additional analysis, missing data for ACR20 response variable will be handled by multiple imputation. Multiple imputation is a simulation-based approach where missing values are replaced by multiple Bayesian draws from the conditional distribution of missing data given the observed data and explanatory variables, creating multiple completed data sets. These completed data sets can then be analyzed using standard methods. Within this analysis, the ACR components will be imputed and response variables will be derived based on the imputed scores. In the multiple imputation analysis, the response status will be imputed based on the individual treatment arm information.

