2.7.4 Supportive analyses

Not applicable.

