5.4.6 Mixed-effects repeated measures model

Change from baseline in log (hsCRP) will be analyzed using mixed-effects model repeated measures (MMRM) with treatment (3 treatment groups), visit, baseline hsCRP, methotrexate usage at baseline (yes, no), and body weight (kg) as explanatory variables. An unstructured covariance structure will be assumed for this model.

SAS code for mixed model:

proc mixed data=aaa; class TRT USUBJID AVISITN; model CHG=TRT AVISITN WEIGHT BASE / s ddfm=kr; lsmeans TRT*AVISITN / diff cl; repeated AVISITN / type=un subject=USUBJID; run;

In case the MMRM model does not converge the following sequential steps will be used: 1. change ddfm=kr to ddfm=bw. If still no convergence, perform step 2.

2. change type=un to type=cs.

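### Week 16 change in DAS28-CRP, PASDAS, SF-12 and HAQ-DI rests on LOCF ANCOVA alone; the resulting error depends on dropout by arm, and no sensitivity analysis is planned to show it

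*SAP*

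**What the plan says.** Protocol 9.5.1 sets the model: "Secondary efficacy variables 9-12 will be analyzed at each time point by an analysis of covariance (ANCOVA) model". Variables 9–12 are DAS28-CRP, PASDAS, SF-12 and HAQ-DI. The same section then states "Missing data will be imputed using the last-observation-carried-forward (LOCF) method", and SAP 2.7.3 repeats the rule: "Missing data for continuous variables will be imputed using the last-observation-carried-forward (LOCF) method". SAP 2.7.2 and 2.11 apply the ANCOVA at each visit up to Week 16. The whole content of SAP 2.7.4, Supportive analyses, is "Not applicable".

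Two other outcomes are treated differently. For the primary endpoint, SAP 2.5.3 adds to non-responder imputation: "In an additional analysis, missing data for ACR20 response variable will be handled by multiple imputation". For change in log hsCRP, SAP 5.4.6 specifies an MMRM with unstructured covariance.

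For a patient who stops treatment in Period 1, protocol section 6 (Premature Discontinuation) says the end-of-period visit "must be performed approximately four weeks after the last dose of study treatment".

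**The concern.** The secondary objectives ask about change at Week 16, and protocol 3.3 justifies 16 weeks as the time by which the arms separate clinically. If response is still developing, a value from Week 4 or Week 8 is not a Week 16 value. LOCF nevertheless enters it as one, with the same weight as a real observation.

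Dropout need not be balanced. Protocol 5.5.9 tells investigators to stop treatment for lack of improvement or worsening, which could remove more placebo patients. Adverse events could remove more active patients. Values can also be missing without dropout: SAP 2.1.2 allows gaps in visits, protocol Appendix 10 forfeits an unfinished questionnaire, and Appendix 8 gives no HAQ score when fewer than six categories are answered.

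At stake are four secondary comparisons for each dose, with p-values that depend on one untested assumption. Where missing data could change a result, the reader would have no way to see it.

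**Working it through.** **1. The plan's own figure.** There is no sample size for these endpoints. The ACR20 calculation (50% v 20%, 2:1, two-sided 0.05, power 0.90, continuity-corrected) reproduces exactly at 88 and 44. Inflated for 10% loss, 88/0.9 = 97.8 and 44/0.9 = 48.9, so 98 + 98 + 49 = 245, stated as about 250. Only the 10% loss and the arm sizes (100 v 50) are used below.

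**2. Which value is carried.** With the day windows in SAP Table 2-1, a last dose at Week 4 (Day 29) puts the discontinuation visit near Day 57, in the Week 8 window. A last dose at Week 8 (Day 57) puts it near Day 85, in the Week 12 window. Both are carried to Week 16. Only a last dose at Week 12 (Day 85 + 28 = 113) yields a Week 16 value.

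**3. Closed form, dropout at random.** Let A and P be the mean Week 16 improvement on active and placebo in baseline SDs, dA and dP the dropout, and f the share of the Week 16 improvement reached at the last visit. Then

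LOCF difference = A[1 − dA(1 − f)] − P[1 − dP(1 − f)], so error = −(1 − f)(A·dA − P·dP).

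Assume A = 0.8 and P = 0.3 (true difference 0.50). Example: 10% in both arms and f = 0.5 gives 0.8 × 0.95 − 0.3 × 0.95 = 0.475.

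| Dropout active / placebo | f = 0.25 | f = 0.50 | f = 0.75 |
|---|---|---|---|
| 10% / 10% | 0.463 (−7.5%) | 0.475 (−5.0%) | 0.488 (−2.5%) |
| 20% / 5% | 0.391 (−21.7%) | 0.428 (−14.5%) | 0.464 (−7.3%) |
| 5% / 20% | 0.515 (+3.0%) | 0.510 (+2.0%) | 0.505 (+1.0%) |

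The error favours the drug only when P·dP exceeds A·dA. Here that means placebo dropout more than 0.8/0.3 = 2.7 times active dropout.

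**4. Simulation.** 100 active v 50 placebo, with A and P as above. Also assumed: 15/45/70/88/100% of the effect at Weeks 1/4/8/12/16, between-visit correlation 0.6, and dropout either random or likelier after a poor last value. Differences are shown as benefit; percentages come from unrounded values.

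| Dropout active / placebo | LOCF ANCOVA | Repeated measures |
|---|---|---|
| 10% / 10% | 0.48 (4–5% too small) | 0.50 |
| 20% / 20% | 0.45 (about 10% too small) | 0.50 |
| 20% / 5% | 0.44 to 0.39 (13–22% too small) | 0.51 to 0.49 |
| 5% / 20% | 0.51 to 0.55 (3–9% too large) | 0.50 |

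**5. Other assumptions.** With a true difference of 0.80 and 50/75/90/100% of the effect at Weeks 4/8/12/16, about 10% random dropout gives LOCF 0.78 (0.02/0.80 = 2.5% too small). Dropout of 14% active, mostly early, v 6% placebo gives 0.73 (0.07/0.80, about 9%). Dropout driven by poor response leaves LOCF close to 0.80. With A = 0.8 and no placebo improvement, 20%/5% gives 9.8–14.0% too small, and 5%/20% gives between 2.2% too small and 1.7% too large. The 3–9% excess therefore needs some placebo improvement.

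**6. False positives.** With A = P = 0.5, equal dropout gives 4.2–5.0% rejection, so no inflation. Dropout of 5%/20% gives 7.0% (random) and 7.6% (after poor values). As a check, take rejection = Φ(−c + δ) + Φ(−c − δ), with δ = bias/SD and c = 1.96 × model SE/SD. Random: δ = 0.039/0.160 = 0.244, c = 1.96 × 0.157/0.160 = 1.923, giving 6.2%. After poor values: δ = 0.077/0.162 = 0.475, c = 1.96, giving 7.6%. Simulation error is at least √(0.05 × 0.95/2,000) = 0.5 points, so about 7% is a fair summary.

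**The case against.** The only dropout figure in the documents is 10%, not split by arm. At that level, with balance, the error is a few per cent. The larger figures need imbalances that were assumed. This stands, and it rules out saying that the Week 16 results are biased.

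The discontinuation visit makes many carried values genuine end-of-treatment assessments. That is true, but step 2 shows most still belong to an earlier week. The objectives are worded for Week 16, and neither document names last on-treatment status as the target. MMRM does aim at a different quantity, the effect had patients continued, and the plan should say which it wants.

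A reader might infer that single imputation materially understates the standard errors. The calculations do not support that. At 10% dropout in both arms (A = 0.8, P = 0), LOCF model SEs were 0.157 and 0.162 against its own sampling SDs of 0.160 and 0.159, with coverage of 94.2% and 95.4%.

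A reader might also infer that the hsCRP code can simply be reused. It cannot. Its model statement is "model CHG=TRT AVISITN WEIGHT BASE / s ddfm=kr": there is no treatment-by-visit term, although the LSMEANS line asks for those means, and methotrexate use is missing, although the text lists it.

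The good performance of repeated measures was shown only for random dropout or dropout depending on observed values, where it should do well. Departures from missing at random were not tested.

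Finally, the SAP's update log has entries after the Week 16 lock, when the analysts were to be unblinded. Replacing the main analysis then would be post hoc. Section 2.13 is also absent from the available SAP text, so anything planned there could not be seen.

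**Conclusion.** The point holds as a conditional one. LOCF ANCOVA is the only planned inferential analysis for the four continuous secondary variables. The observed-data summaries in SAP 2.7.2 are descriptive and do not test the Week 16 comparison.

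The likely error is small if dropout is near 10% and balanced: about 2–5% too small in the simulations, and 7.5% in the closed form if every dropout leaves with a quarter of the effect. It grows to about 10–22% too small if the active arm loses more patients. It reverses to 3–9% too large, with type I error near 7%, if placebo loses far more and placebo patients also improve. LOCF therefore cannot be defended as always conservative. Response curves, correlation and dropout splits are all assumptions.

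The documents do not support the stronger conclusion that these comparisons are wrong, or wrong in a known direction. Nor do they support any doubt about the primary endpoint: ACR20 uses non-responder imputation with multiple imputation as an additional analysis. The defect is worth correcting but not critical.

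**What to change.** Analyse variables 9–12 through Week 16 by MMRM, using the visits at which each is scheduled. Include treatment, visit, treatment-by-visit, baseline, baseline-by-visit, methotrexate use and body weight, with unstructured covariance and Week 16 contrasts of each dose with placebo. Report the LOCF ANCOVA alongside. Add one check on departures from missing at random, for example a delta-adjusted or placebo-based imputation for patients who leave the active arms. State how patients with no post-baseline value are handled.

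Correct the SAP 5.4.6 code before adapting it: add the treatment-by-visit term, the baseline-by-visit term and methotrexate use, which also belongs in the CLASS statement.

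Record the change in SAP section 4, which at present lists none. If it is adopted after the Week 16 lock, keep LOCF ANCOVA as the prespecified result and present MMRM as a labelled post hoc sensitivity analysis.

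The cost is a documented departure from the protocol's stated method and modest extra programming. No new data are needed.
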